Describe the primary and secondary study endpoints:

Primary Outcomes: Pain scores as assessed by validated outcomes measures, compliance over 4 weeks, durability of the device (do the bubbles hold up or require replacement).

Secondary Outcomes: Satisfaction with using the device, difficulties with the use of the device.

4. Provide a description of the following study timelines:

Duration of an individual subject's active participation:

Cohort 1: 4 Weeks

Cohort 2: 3 Months

Duration anticipated to enroll all subjects:

6 months

Estimated date for the investigator to complete this study (complete primary analyses):

6/30/2020

5. List the inclusion criteria:

Patients meeting the following criteria will be eligible to participate in the study:

- 1. Aged 18 years or older and able to provide informed consent
- 2. Subjects with foot pain due to forefoot or heel fat pad atrophy or chronic plantar fasciitis as defined by heel pain for greater than 6 months and failed non-surgical therapy
- 3. Willing and able to comply with follow up examinations

6. List the exclusion criteria:

Patients with the following characteristics will be excluded from participating in the study:

- 1. Concurrent injury to the lower extremity that would effect gait
- 2. Open foot ulcerations, fractures, or diagnosis of osteomyelitis of the feet
- 3. Surgical foot intervention in the last 6 months
- 4. Diagnosis of pregnancy or the intent of the participant to become pregnant during participation in this study
- 5. Neuropathy

- 6. Any issue that per the physician's determination would render the patient not appropriate to continue participation in the study (compliance, change in physical status, etc.)
- 7. Will children or any gender, racial or ethnic subgroups be explicitly excluded from participation?
 - Yes O No
 - * Identify the subgroups and provide a justification:

As foot pain due to forefoot or heel fat pad atrophy or chronic plantar fasciitis generally is not common in children, we will be limiting our population to adults 18 years of age or older.

8. Describe the power analysis used and cite your method of statistical analysis. If a power analysis is not possible, thoroughly justify the sample size required for the study, including appropriate literature citation (alternatively provide page reference in attached protocol):

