- Manchester Foot and Ankle Disability Index to assess subject foot pain/discomfort
- Pittsburgh Foot Survey to assess subject pain, activity, life satisfaction/quality of life
- Mayo Clinical Scoring System questionnaire (MAYO) to assess subject pain, activity, and function (Investigator Rated)
- American Orthopaedic Foot and Ankle Society questionnaire (AOFAS) to assess subject pain and function (Investigator Rated)
- 2.) 2D Photographs of both feet will be performed for a visual baseline assessment of skin.
- 3.) Collection of subject's vital signs (Temp, HR, Resp., BP), medication profile, allergies, weight, BMI calculation and adverse event collection and reporting.
- 4.) Diary cards with instruction to start entry on the diary card 24 hours after the screening visit to continue through Visit 2 (Month 1) and be placed to study chart. The subject will be instructed to document self-assessment of the following events pertaining to the feet: Pain, Bruising, Redness of the skin, Itching, Swelling, Bleeding, Other (any concerns/issues not listed). The subject will be instructed to identify on the diary card the location, date, and day of each documented event. Unresolved events at Visit 2 will be carried over for documentation to the adverse event log.

5.) Offload Device Distribution to remain in use at all times during ambulation. Devices will be provided for both feet to maintain symmetry and gait stability between the two feet. One pair of devices will be given for use in shoe gear, and one pair will be given for use in a slide in the shower. A device instruction sheet will also be provided to the participants for reference.

48 Hour (+/- 1 Day) Phone Call

The study coordinator will call the subject 48 hours after the screening visit and eligibility determination. This phone call is to assess if there are any questions or concerns with the fit and feel of the PopSole device. If there are any issues that the subject may be experiencing the study coordinator will have an investigator or co-investigator reach out to the subject. The coordinator will be working off of a phone script, to ensure that all aspects of wearing the device have been addressed.

Follow up Visits:

Visit 1 (Week 2) with (+/- 7days) study window:

This visit will take approximately 1 hour and will take place at the Isaly's Medical Building- UPMC Aesthetic Surgery Center and/or UPMC Lemieux Sports Medicine Complex with the physician investigator and research team.

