- a.) Collection of vital signs (Temp, HR, Resp., BP), medication profile, allergies, weight, and BMI calculation.
- b.) Limited physical exam with a foot exam completed by the PI and /or the Co-investigator
- c.) Adverse Event Reporting collecting any problems or symptoms or significant events that have occurred since the screening/baseline visit, including any unscheduled hospital or primary care provider visits. Review Medical Records for changes in medical/surgical history.
- d.) Collection and distribution of diary cards
- e.) 2D Photographs of both feet for a visual baseline assessment of the skin and soft tissue thickness.
- f.) Foot Assessment Questionnaires: (FAAM, Mayo Clinical Scoring System, AOFAS Score, Manchester, and Pittsburgh Foot Survey) pertaining to foot pain and activity assessments.
- g.) Device survey questions about the fit and feel of the device

Visit 2 (Month 1) with (+/-7 days) study window:

This visit will take approximately 1 hour and will take place at the Isaly's Medical Building- UPMC Aesthetic Surgery Center and/or UPMC Lemieux Sports Medicine Complex with the physician investigator and research team.

- a.) Collection of vital signs (Temp, HR, Resp., BP), medication profile, allergies, weight, and BMI calculation.
- b.) Limited physical exam with a foot exam completed by the PI and /or the Co-investigator
- c.) Adverse Event Reporting collecting any problems or symptoms or significant events that have occurred since follow up visit 1, including any unscheduled hospital or primary care provider visits. Review Medical Records for changes in medical/surgical history.
- c.) Collection of diary cards
- d.) 2D Photographs of both feet for a visual assessment of your skin and soft tissue

thickness

- e.) Foot Assessment Questionnaires: (FAAM, Mayo Clinical Scoring System, AOFAS Score, Manchester, and Pittsburgh Foot Survey) pertaining to foot pain and activity assessments.
- f.) Collection of diary cards
- g.) Device survey questions about the fit and feel of the device
- h.) PopSole™ Device removal

COHORT 2:

Patients presenting with foot pain (pain in the forefoot, heel or plantar fascia) will be offered inclusion in the clinical trial. Information about the study will be provided at the time of candidate review. Once informed consent has been obtained then study procedures will be implemented for eligibility determination.

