1. * Describe your plan to periodically evaluate the data collected regarding both harms and benefits to determine whether subjects remain safe. The plan might include establishing a data monitoring committee and a plan for reporting data monitoring committee findings to the IRB and the sponsor: The Data Safety and Monitoring Plan for this research study will consist of a Local Data and Safety Monitoring Plan that will be implemented by the Principal Investigator to ensure that there are no changes in the risk/benefit ratio during the course of the study and that confidentiality of research data is maintained. This DSMB will consist of the PI, Co- Investigators and study personnel who will meet and discuss monthly the study (e.g., study goals and modifications of those goals; subject recruitment and retention; progress in data coding and analysis: documentation, identification of adverse events or research subject complaints: violations of confidentiality) and address any issues or concerns at that time. Minutes will be kept for these meetings and will be maintained in the study binder. Any instances of adverse events will be reported immediately to the University of Pittsburgh IRB in accordance with IRB Guidelines.

The annual IRB renewal for this study will include a summary report of the Data and Safety Monitoring Plan findings from the study for the prior year. We will include the following information at the time of the IRB renewal: the frequency of the monitoring, the dates that the monthly meetings took place, a summary of the cumulative adverse events, external factors or relevant information that might have an impact on the safety or ethics of the study, and final conclusions regarding changes to the anticipated risk/benefit ratio to study participation and final recommendations related to the continuation, changing, or termination of the study.

2. * Describe your plan for sharing data and/or specimens:

Information obtained from this study may be shared with other investigators who are interested in the care of the foot. However, information will be de-identified, shared without any subject identifiers.

The investigators may continue to use and disclose, for the purposes of this research, de-identified information related to participation in this research study indefinitely. It is University of Pittsburgh policy to maintain research records and data for at least 7 years following final reporting or publication of a project.

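### Diary rule sends any unresolved foot pain at Visit 2 to the adverse event log, with no test separating persisting entry pain from new or worsened pain

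*Combined protocol and SAP*

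**What the plan says.** Inclusion criterion 2 (Study Design, item 5) admits "Subjects with foot pain due to forefoot or heel fat pad atrophy or chronic plantar fasciitis". Pain is also an efficacy measure; Study Design, item 3 begins "Primary Outcomes: Pain scores as assessed by validated outcomes measures, compliance over 4 weeks".

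In Research Activities, the device is issued at the screening/baseline visit. Item 4 of the screening procedures, worded alike for Cohorts 1 and 2, has participants "start entry on the diary card 24 hours after the screening visit" and then "document self-assessment of the following events pertaining to the feet: Pain, Bruising, Redness of the skin, Itching, Swelling, Bleeding, Other". For each event they give its location, date and day. The item ends: "Unresolved events at Visit 2 will be carried over for documentation to the adverse event log".

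Adverse events are also collected at each visit. At Visit 1 this is described as "Adverse Event Reporting collecting any problems or symptoms or significant events that have occurred since the screening/baseline visit".

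Data Safety and Monitoring, item 1 says: "Any instances of adverse events will be reported immediately to the University of Pittsburgh IRB in accordance with IRB Guidelines". It also promises a cumulative adverse event summary at each annual renewal, with conclusions on the risk/benefit ratio.

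**The concern.** The symptom that qualifies a person for the trial is also a diary event, and the only stated condition for moving it to the adverse event log is that it has not resolved. Chronic foot pain may well ease without vanishing in four weeks. A participant in that position is a partial success on the pain questionnaires and an adverse event in the log.

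What is at stake is how the safety record can be read. If the log mixes participants who still have their entry condition with participants who have new or aggravated pain, the number of pain entries says little about either group. There is no control arm to supply a background rate of persisting pain, so the comparison with baseline has to come from a stated rule. Pain is also a symptom through which some listed device risks might show, such as irritation, failure to offload the right area, or a feeling of asymmetry.

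**Working it through.** The plan has no figure to reproduce here, and the point rests on no sample size, power or rate. The check is to put the provisions side by side and follow them.

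**Inputs**

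1. Foot pain at entry: required of everyone (Study Design, item 5). Planned enrolment is 20 (Study Design, item 1).
2. Device start: screening/baseline visit (Research Activities, both cohorts).
3. Diary start: 24 hours after that visit, so the diary holds no pre-device entry.
4. Diary item: pain of the feet, with no condition that it be new or worse.
5. Carry-over condition: unresolved at Visit 2. No exception for pre-existing pain is stated.
6. Adverse event definition, severity grade or relatedness assessment: none in the text supplied.
7. Data that could supply a baseline comparison: the foot exam and pain questionnaires, both done at baseline and at Visits 1 and 2.

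**Applying the rule**

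Take four hypothetical participants who enter with heel pain and record pain in the diary:

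| Status at Visit 2 | Logged under the stated rule? | New or worse than baseline? |
|---|---|---|
| Heel pain improved, not gone | Yes | No |
| Heel pain unchanged | Yes | No |
| Heel pain worse | Yes | Yes |
| New forefoot pain | Yes | Yes |

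All four are logged, and nothing in the stated rule marks the first two as different from the last two. The only pain kept out by the rule is pain that has gone.

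**Can the trial's own data tell them apart?** Yes, in large part. Diary location can point to a new site. The repeated exams and questionnaires allow a within-person check for worsening. What is missing is a provision that these data be used to classify diary pain before it enters the log, and an explicit per-foot record of the entry pain sites to compare against.

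**Size.** Because all 20 planned participants have foot pain at entry, the number meeting the rule could lie anywhere from 0 to 20. The documents give no rate of persisting pain at Month 1 and no rate of new or worsened pain, so the range cannot be narrowed from them.

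**Cohort 2.** Item 4 ends the diary, and applies the carry-over, at Visit 2 (Month 1). Yet cards are handed out again at Visit 2 and collected at Visits 3 and 4. No carry-over rule is stated for events open at Visit 4 or first recorded after Visit 2.

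**The case against.** - **The trial already knows each participant's baseline.** There is an orthopedic foot exam, a set of pain questionnaires and adverse event collection at the screening visit itself, and the device is customised to the painful area. This stands, and it defeats a stronger reading that a reader might infer: that new or device-caused pain cannot be separated from entry pain. It does not repair the carry-over sentence, which turns only on whether the event has resolved.
- **Logging is not attribution.** A reader might infer that persisting pain is being counted as harm from the device. The documents do not support that: the event is documented in the log, and no passage attributes log entries to the device.
- **The forms are not in the documents.** The diary card and the adverse event log may carry severity, relatedness or baseline-comparison fields. This is a real limit on certainty, though the protocol's own sentence would still need to agree with such fields.
- **The text can be read more gently.** Asking for the date of each event may suggest discrete episodes after device issue, and visit-level collection may simply complement the diary. Both readings are possible; neither is stated.
- **Little depends on it.** No adverse event rate is an endpoint or has a planned analysis, IRB reporting follows guidelines not reproduced here, and over-inclusive logging is cautious in a small study of a device described as minimal risk. This limits the consequence to the safety record. It does not make that record interpretable.

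**Conclusion.** The point holds as a defect in a stated rule. Followed literally, the carry-over sentence in both cohorts puts persisting or improved entry-site pain into the adverse event log and the IRB summary, alongside new or worsened pain, and the plan gives no criterion for separating them.

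The conclusion assumes that participants enter their ongoing pain in the diary as the item invites, and that no form outside the documents adds a baseline test.

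It is tempting to attach an inflation factor to the pain count. Any such figure would be a ratio of two assumed rates, neither found in the documents, and no adverse event rate is planned for analysis. The size is therefore left unquantified. The planned analysis of pain and function is not biased by this. The change is worth making because it is cheap and corrects an input to the risk/benefit review.

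**What to change.** 1. Keep the diary pain item as it is. Asking participants to filter pain by their own recall of what is worse could lose aggravation at the entry site.
2. At the baseline foot exam, before the device is issued, record the pain site or sites for each foot.
3. Amend the carry-over sentence in screening item 4 for both cohorts. The investigator carries diary pain to the adverse event log only if it is at a new site or worse than baseline, judged against the baseline exam and questionnaires. Unchanged or improved entry-site pain is reported through the questionnaires.
4. For Cohort 2, reconcile the Visit 2 cut-off with diary collection through Visit 4.

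The cost is one baseline line on the form, an edit to one sentence in each cohort's item 4, and the Cohort 2 reconciliation. The small downside is that the investigator must judge what counts as worse.

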Should the subject complete the informed consent process and screening procedures, the duration of time to complete is estimated to take approximately 1-2 hours and will include the following research procedures:

- 1.) Obtain Informed Consent to be completed by the Principal Investigator (PI) or designated Co-Investigator. Once completed the subject will be allocated a subject ID number. This number will be the unique identifier for the subject during his/her trial participation.
- 2.) Performance of a limited physical exam, inclusive of participant's foot exam with a gait and shoe gear evaluation to be completed by the PI and /or Co-investigator. Any prior foot injuries or previous foot ulcerations/skin breakdown will be assessed. The foot exam will include a vascular, neurologic, dermatologic and orthopedic baseline assessment. As part of the exam (for example, related to diagnosing plantar fasciitis), an ultrasound may be performed in the clinics per the investigators' discretion.
- 3.) Medical and surgical history collection: Past medical and surgical history will be collected by referral report or subject report.

Should the physician require additional information for review to confirm study eligibility, the subject may be asked to obtain and provide medical records to assist with the PI's review.

- 4.) Collection of subject's vital signs (Temp, HR, Resp., BP), medication profile, allergies, height, weight, and BMI calculation.
- 5.) Collection of demographic information to include subject's date of birth, gender, race, ethnicity, education, and smoking history.

ELIGIBILITY DETERMINATION: The Principal Investigator and/or in consultation with the co-investigators will determine subject eligibility to participate in the study based on the inclusion/ exclusion criteria.

All subjects will receive the PopSole™ offloading device at the screening/baseline visit, be asked to wear it for 4 weeks, and will be asked to return for an in-person

evaluation at V1 (Week 2), V2 (Week 4), V3 (Week 8) and a completion study visit at V4 (Week 12). There will also be a phone call 48 hours after the screening visit, At week 6 and at Week 10 to ensure that the patient has no issues or concerns with wearing the device.

Subjects will complete the following screening research procedures:

- 1.) Baseline reported outcome measures (PROMs) questionnaires and surveys that will take approximately 25 minutes to complete:

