- Foot and Ankle Ability Measure (FAAM) questionnaire to assess subject ADL and function ability
- Manchester Foot and Ankle Disability Index to assess subject foot pain/discomfort
- Pittsburgh Foot Survey to assess subject pain, activity, life satisfaction/quality of life
- Mayo Clinical Scoring System questionnaire (MAYO) to assess subject pain, activity, and function (Investigator Rated)
- American Orthopaedic Foot and Ankle Society questionnaire (AOFAS) to assess subject pain and function (Investigator Rated)
- 2.) 2D Photographs of both feet will be performed for a visual baseline assessment of skin.
- 3.) Collection of subject's vital signs (Temp, HR, Resp., BP), medication profile, allergies, weight, BMI calculation and adverse event collection and reporting.
- 4.) Diary cards with instruction to start entry on the diary card 24 hours after the screening visit to continue through Visit 2 (Month 1) and be placed to study chart. The subject will be instructed to document self-assessment of the following events pertaining to the feet: Pain, Bruising, Redness of the skin, Itching, Swelling, Bleeding, Other (any concerns/issues not listed). The subject will be instructed to identify on the diary card the location, date, and day of each documented event. Unresolved events at Visit 2 will be carried over for documentation to the adverse event log.
- 5.) Offload Device Distribution to remain in use at all times during ambulation. Devices will be provided for both feet to maintain symmetry and gait stability between the two feet. One pair of devices will be given for use in shoe gear, and one pair will be given for use in a slide in the shower. A device instruction sheet will also be provided to the participants for reference.

48 Hour (+/- 1 Day) Phone Call study window:

The study coordinator will call the subject 48 hours after the screening visit and eligibility determination. This phone call is to assess if there are any questions or concerns with the fit and feel of the PopSole device. If there are any issues that the subject may be experiencing the study coordinator will have an investigator or co-investigator reach out to the subject. The coordinator will be working off of a phone script, to ensure that all aspects of wearing the device have been addressed.

Follow up Visits:

Visit 1 (Week 2) with (+/- 7 days) study window:

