This visit will take approximately 1 hour and will take place at the Isaly's Medical Building- UPMC Aesthetic Surgery Center and/or UPMC Lemieux Sports Medicine Complex with the physician investigator and research team.

- a.) Collection of vital signs (Temp, HR, Resp., BP), medication profile, allergies, weight, and BMI calculation.
- b.) Limited physical exam with a foot exam completed by the PI and /or the Co-investigator
- c.) Adverse Event Reporting collecting any problems or symptoms or significant events that have occurred since the screening/baseline visit, including any unscheduled hospital or primary care provider visits. Review Medical Records for changes in medical/surgical history.
- d.) Collection and distribution of diary cards
- e.) 2D Photographs of both feet for a visual baseline assessment of the skin and soft tissue thickness.
- f.) Foot Assessment Questionnaires: (FAAM, Mayo Clinical Scoring System, AOFAS Score, Manchester, and Pittsburgh Foot Survey) pertaining to foot pain and activity assessments.
- g.) Device survey questions about the fit and feel of the device

Visit 2 (Month 1) with (+/-14 days) study window:

This visit will take approximately 1 hour and will take place at the Isaly's Medical Building- UPMC Aesthetic Surgery Center and/or UPMC Lemieux Sports Medicine Complex with the physician investigator and research team.

- a.) Collection of vital signs (Temp, HR, Resp., BP), medication profile, allergies, weight, and BMI calculation.
- b.) Limited physical exam with a foot exam completed by the PI and /or the Co-investigator
- c.) Adverse Event Reporting collecting any problems or symptoms or significant events that have occurred since follow up visit 1, including any unscheduled hospital or primary care provider visits. Review Medical Records for changes in medical/surgical history.
- c.) Collection of diary cards
- d.) 2D Photographs of both feet for a visual assessment of your skin and soft tissue thickness
- e.) Foot Assessment Questionnaires: (FAAM, Mayo Clinical Scoring System, AOFAS Score, Manchester, and Pittsburgh Foot Survey) pertaining to foot pain and activity assessments.
- f.) Collection and distribution of diary cards
- g.) Device survey questions about the fit and feel of the device

Week 6 Phone Call (+/-14 days) study window:

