The study coordinator will call the subject during week 6. This phone call is to assess if there are any questions or concerns with the fit and feel of the PopSole device. If there are any issues that the subject may be experiencing the study coordinator will have an investigator or co-investigator reach out to the subject. The coordinator will be working off of a phone script, to ensure that all aspects of wearing the device have been addressed.

Visit 3 (Month 2) with (+/-14 days) study window:

This visit will take approximately 1 hour and will take place at the Isaly's Medical Building- UPMC Aesthetic Surgery Center and/or UPMC Lemieux Sports Medicine Complex with the physician investigator and research team.

- a.) Collection of vital signs (Temp, HR, Resp., BP), medication profile, allergies, weight, and BMI calculation.
- b.) Limited physical exam with a foot exam completed by the PI and /or the Co-investigator
- c.) Adverse Event Reporting collecting any problems or symptoms or significant events that have occurred since follow up visit 1, including any unscheduled hospital or primary care provider visits. Review Medical Records for changes in medical/surgical history.
- c.) Collection of diary cards
- d.) 2D Photographs of both feet for a visual assessment of your skin and soft tissue thickness
- e.) Foot Assessment Questionnaires: (FAAM, Mayo Clinical Scoring System, AOFAS Score, Manchester, and Pittsburgh Foot Survey) pertaining to foot pain and activity assessments.
- f.) Collection of diary cards
- g.) Device survey questions about the fit and feel of the device

Week 10 Phone Call (+/-14 days) study window

The study coordinator will call the subject during week 6. This phone call is to assess if there are any questions or concerns with the fit and feel of the PopSole device. If there are any issues that the subject may be experiencing the study coordinator will have an investigator or co-investigator reach out to the subject. The coordinator will be working off of a phone script, to ensure that all aspects of wearing the device have been addressed.

Visit 4 (Month 3) with (+/-14 days) study window:

This visit will take approximately 1 hour and will take place at the Isaly's Medical Building- UPMC Aesthetic Surgery Center and/or UPMC Lemieux Sports Medicine Complex with the physician investigator and research team.

- a.) Collection of vital signs (Temp, HR, Resp., BP), medication profile, allergies, weight, and BMI calculation.

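### Cohort 2 is told to wear the device for 4 weeks, but its procedures imply wear until removal at Visit 4 (Month 3), so Visits 3 and 4 may be on-device or post-device

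*Combined protocol and SAP*

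**What the plan says.** The wear period for Cohort 2 is stated once, in the eligibility paragraph of Research Activities: "All subjects will receive the PopSole™ offloading device at the screening/baseline visit, be asked to wear it for 4 weeks". The Cohort 1 paragraph uses the same wording. Study Aims, item 2, also describes a 4-week trial of the device, without separating the cohorts.

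The rest of the Cohort 2 text runs past 4 weeks:

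- The same eligibility paragraph schedules visits at Weeks 8 and 12, and calls "At week 6 and at Week 10 to ensure that the patient has no issues or concerns with wearing the device".
- The distribution step reads "Offload Device Distribution to remain in use at all times during ambulation" and gives no end date.
- "Visit 2 (Month 1) with (+/-14 days) study window" lists no removal step. Diary cards are collected and handed out again.
- The later calls are headed "Week 6 Phone Call (+/-14 days) study window" and "Week 10 Phone Call (+/-14 days) study window". Both repeat this sentence: "The coordinator will be working off of a phone script, to ensure that all aspects of wearing the device have been addressed".
- The device survey and the foot questionnaires are repeated at Visits 3 and 4.
- Removal of the device is listed only at Visit 4 (Month 3).

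Study Design, item 4, gives Cohort 2 three months of active participation, which is not a statement about wear. Item 3 names pain, compliance over 4 weeks and durability as primary outcomes.

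**The concern.** A reader who follows the only explicit wear statement stops Cohort 2 at Week 4. A reader who follows the visit procedures stops at Visit 4. No visible text reconciles the two.

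The meaning of the later data depends on the answer. If wear ends at 4 weeks, Week 8 and Week 12 scores show whether any benefit persists after stopping. If wear continues, they show the effect during use. Durability would likewise be tested over 4 weeks or about 12. These are the data that the longer cohort adds to the study.

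**Working it through.** The plan gives no figure for the end of wear, so there is none to reproduce. Its one calculated figure, at least 10 subjects, is not an input here. The check sets the texts side by side and counts days.

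**Conventions.** The device is given at the screening/baseline visit, taken as day 0. Four weeks = 4 × 7 = day 28. The eligibility paragraph equates Visits 3 and 4 with Weeks 8 and 12, so Months 2 and 3 are centred on days 56 and 84.

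**Cohort 2 windows (±14 days, from the visit and call headings), with distance from day 28**

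| Contact | Centre | Window (days) | Days after day 28 |
|---|---|---|---|
| Week 6 call | 42 | 28 to 56 | 0 to 28 |
| Visit 3 | 56 | 42 to 70 | 14 to 42 |
| Week 10 call | 70 | 56 to 84 | 28 to 56 |
| Visit 4 (removal) | 84 | 70 to 98 | 42 to 70 |

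**Gap between the two ends of wear.** Nominal: 84 − 28 = 56 days. Earliest Visit 4: 70 − 28 = 42. Latest: 98 − 28 = 70.

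**Visits affected.** Visit 3 cannot fall before day 42 or Visit 4 before day 70. Under the 4-week text both are post-device at any permitted date. Under the procedures both are on-device. That is 2 of the 4 post-baseline visits.

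**Is the result sensitive to an exact day 28?** The plan calls Visit 2 both Week 4 and Month 1, so 4 weeks may simply mean until that visit. Visit 2 may be held from 28 − 14 = day 14 to 28 + 14 = day 42. Its latest permitted day is no later than the earliest Visit 3 (day 42), so the status of Visits 3 and 4 does not depend on the strict reading.

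**Cohort 1 for comparison.** Visit 2 includes removal and falls on 28 ± 7 = day 21 to 35. The stated period and the removal step differ by at most 7 days and agree at the nominal date. The conflict is specific to Cohort 2.

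**What the analysis uses.** Study Design, item 8, names 3 questionnaire time points and a comparison of baseline with 4 weeks. Neither reaches Week 8 or 12.

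**The case against.** The strongest reply is that the 4-week phrase was carried over from Cohort 1 and that the Cohort 2 procedures show what is meant. Much of this stands. The wording is identical, and the Week 10 call paragraph still refers to Week 6, so some text was evidently copied without full editing. The calls about wearing, the repeated device surveys, the diary cards handed out at Visit 2 and the removal at Visit 4 all lean the same way, and no washout or persistence objective is described. But this remains inference. The 4-week phrase is the only explicit wear instruction for Cohort 2, and Study Aims repeats it. The Cohort 2 diary instruction at distribution also stops at Visit 2, although it concerns foot events rather than wear.

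A second reply, that the consequences are limited, also stands: this is a 20-subject proof-of-concept study, and no stated analysis uses the later visits.

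A reader might infer more than the documents support:

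- *That every 4-week statement contradicts longer wear.* The brief description and the compliance outcome give assessment windows. A 4-week outcome can be measured in a cohort that wears the device for longer.
- *That late Visit 2 data are also post-device.* This needs 4 weeks to mean exactly day 28, which the plan's interchangeable use of Week 4 and Month 1 does not support.
- *That wear status is unrecorded.* The Aim 2 survey is meant to cover compliance, and the accountability records in Devices, item 4, cover subject use. Those forms, the schema, the scripts and the participant instructions are not shown.

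**Conclusion.** The plan contradicts itself on how long Cohort 2 wears the device, and the text is wrong as written. The stated and implied ends of wear are about 56 days apart (42 to 70 with the Visit 4 window). Pain, function and durability at Visits 3 and 4 cannot be classed as on-device or post-device from the visible text.

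The effect is confined to interpreting those two visits. The Week 2 and Week 4 comparisons and the sample-size statement are unaffected. The figures are day counts, not an estimate of bias in any result. They assume that wear starts at the baseline visit and that the Month 2 and Month 3 windows are centred on Weeks 8 and 12. The documents not shown may settle what participants are told in practice.

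**What to change.** 1. Reconcile the Cohort 2 eligibility paragraph, the device distribution step and the Visit 4 removal step in Research Activities, and the 4-week wording in Study Aims, item 2, so that one Cohort 2 wear period is stated. This review does not say which.
2. Check that the participant instructions and phone script agree with it.
3. State in Study Design, item 3, whether the 4-week compliance outcome also applies to Cohort 2.
4. Report each Visit 3 and Visit 4 outcome as on-device or post-device, using the recorded last day of wear. Confirm first that the survey or accountability records hold that date.

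The cost is a few lines of protocol wording and a check of existing materials, plus one date field if the last day of wear is not already captured. If follow-up has finished, the labelling step still applies.
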